#### **9.1.6. End of treatment restaging**

Response to the treatment will be evaluated 1-2 months after the end of the whole treatment and includes the following tests and evaluation:

- Recent clinical history
- Physical examination (size of lymph nodes, sign of organ involvement)
- ECOG performance status
- Chest and abdomen computer tomography; CT of the head and neck at the discretion of the treating physician
- Testicular ultrasound
- CT-PET scan (to be performed three months after radiotherapy) is mandatory according to recent international criteria of response (Cheson et al 2007)
- Hematology (hemoglobin, WBC and differential, Platelets)
- Blood chemistry (AST, ALT, ALP, total bilirubin, creatinine, albumin, serum LDH)
- Clearance creatinine
- Beta-2-microglobulin
- IgA, IgG, IgM
- Additional assessments if necessary according to the local standards and if clinically indicated at the discretion of the treating physician.

#### **9.1.7. Follow-up phase**

After the completion of the end of treatment evaluation all patients will enter in the follow up phase.

The follow up phase will end in case of dead or progressive disease.

During the follow-up phase the following parameters will be evaluated:

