#### **3.2. Study design**

[figure not shown]
The study is divided in 4 phases.

1. Pretreatment (screening) phase of approximately 28 days. Patients will be evaluated, according to the protocol, before to be enrolled in the study by means of the conventional procedures.
2. Open label non randomized multicenter treatment phase. The investigator will assess patient response to therapy using efficacy measurements and disease response criteria. Patients will be evaluated through this phase for possible toxicities and delays in dosing. Dose modifications will be made as required according to dose modification rules. Patients will be treated with six courses of R-CHOP chemotherapy with a twenty-one day rest period between them. Courses 2,3,4 and 5 will be scheduled with the association of intrathecal chemotherapy with Depocyte®.

Patients with progressive disease at any time will be withdrawn from the study.

3. Consolidation phase. Three weeks after the 6th course of R-CHOP chemotherapy, patients will receive two courses of intermediate-dose Methotrexate therapy every two weeks followed, two weeks later, by scrotal prophylactic radiotherapy or involved field radiotherapy (but can be planned concomitantly to R-CHOP in patients with bilateral disease).
4. Follow-up phase. Patients will be followed for disease progression and survival until the end of the study which is expected to be 36 months after the last patients enrolled into the study completed the treatment. For OS determination information will be required up to 5 years.

The study design is presented in the figure below.

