# 9. STUDY EVALUATIONS

## 9.1. Study Procedures

### 9.1.1. Overview

Patients participation will include:

1. The pretreatment (screening) phase will be 30 days for all laboratory tests and radiographic imaging phase and up to 60 days for orchectomy and bone marrow evaluation.
2. The open label treatment phase will extend from the first day of the first course of R-CHOP to a maximum of 6 courses.
3. The consolidation phase will extend from the first day of the first course of Intermediate-dose MTX to the end of radiotherapy.
4. The follow-up phase will begin after the completion of the consolidation phase. Follow-up will continue until disease progression (PD), patient withdrawal, death or the study completion (expected to be 36 months from the date of the last patient's end of therapy).

Hematology results must be available and reviewed by the investigator to evaluate for possible hematological toxicity.

All subjects will be monitored for adverse events throughout the study and for 30 days after the end of treatment.

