#### **9.1.4. Intermediate evaluations (after third course of R-CHOP)**

- Physical examination (size of lymph nodes, signs of organ involvement)
- ECOG performance status
- Hematology (hemoglobin, WBC and differential, Platelets)
- Blood chemistry (AST, ALT, ALP, total bilirubin, creatinine, albumin, serum LDH)
- Chest and abdomen computer tomography; CT of the head and neck at the discretion of the treating physician
- Testicular ultrasound
- Additional assessments if necessary according to the local standards and if clinically indicated at the discretion of the treating physician.
- Interim CT-PET scan is advisable, if previously positive, according to local policy but it is not mandatory.

All patients with disease in CR, PR will continue the trial.

All patients in SD/PD will be withdrawn from the study and evaluated as treatment failure

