## **10. SUBJECT COMPLETION / WITHDRAWAL**

### **10.1. Completion**

A subject will be considered as having completed the study if he/she has completed all assessments at week 30 of the [open label] treatment phase.] [Subjects who discontinue study treatment due to lack of efficacy are also considered to have completed the study.]

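### The protocol both ends follow-up at progression and requires survival data to 5 years, so 3-year OS may be biased upward; a smaller problem is that PFS censors stable-disease patients at removal

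*Combined protocol and SAP*

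**What the plan says.** **Follow-up ends at progression.** Section 9.1.7: "The follow up phase will end in case of dead or progressive disease". Section 9.1.1, item 4: "Follow-up will continue until disease progression (PD), patient withdrawal, death or the study completion".

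**Patients leave the study at progression, non-response or treatment stop.** Section 3.2, item 2, repeated in section 6.1.1: "Patients with progressive disease at any time will be withdrawn from the study". Section 9.1.4, on the evaluation after the third course: "All patients in SD/PD will be withdrawn from the study and evaluated as treatment failure". Section 10.3 lists stopping study treatment among the reasons for withdrawal from the study. It mentions only final assessments and adds an if-applicable qualifier.

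**Survival follow-up continues.** Section 3.2, item 4: "Patients will be followed for disease progression and survival until the end of the study", expected 36 months after the last patient completes treatment, and "For OS determination information will be required up to 5 years".

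**Completion has another meaning.** Under section 10.1 a patient has completed the study if he "has completed all assessments at week 30", and "Subjects who discontinue study treatment due to lack of efficacy are also considered to have completed the study".

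**Endpoints.** Section 2.2 names 3-year OS, PFS and EFS as secondary objectives, with PFS and EFS set against historical treatment. Section 9.3.1 counts death from any cause for OS and censors survivors at last contact. Its PFS paragraph says that where non-response without progression leads to another therapy, the patient is censored at that point. Its EFS definition counts stopping treatment for any reason as an event.

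**The concern.** A site cannot tell from the protocol whether it must keep collecting survival status once a patient progresses or stops treatment. A site that follows sections 9.1.1, 9.1.7 and 10.3 complies with the protocol and still sends no further survival data. Its patients are then censored for OS close to progression. That censoring is informative, because the risk of death is probably higher after progression than before. The Kaplan-Meier estimate of 3-year OS would then probably be too high, and data that were never collected cannot be recovered at the analysis. If sites read the text differently, the OS estimate mixes two follow-up policies.

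The PFS question is similar but smaller. Section 6.2.1 removes patients without a response after three cycles and has them considered for other therapies, so this trial meets the condition in the PFS paragraph. The same stable-disease patient is a treatment failure in section 9.1.4 and a censored observation for PFS, which favours the regimen in an endpoint compared with history.

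**Working it through.** **Step 1: set the sections side by side.**

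| Situation | Sections that stop | Sections that continue |
|---|---|---|
| Progression | 3.2 item 2, 6.1.1, 9.1.1, 9.1.7 | 3.2 item 4 |
| Stable disease after course 3 | 6.2.1, 9.1.4 | 3.2 item 4 |
| Treatment stopped for another reason | 10.3 | 3.2 item 4 |

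Section 3.2 conflicts with itself. Section 9.1.7 schedules visits at months 3 to 36 for patients who have had the end-of-treatment evaluation. Neither that section nor Attachment 9 schedules contact after progression, after withdrawal or after month 36. A patient who stops for lack of efficacy is withdrawn under 9.1.4 but has completed the study under 10.1.

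**Step 2: size of the OS bias.** The documents give no figure for this, so what follows is an illustration.

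- Inputs: 3-year OS 88% and EFS 78%, the preliminary results of the prior prospective study (section 1.1.1); 35 patients (synopsis).
- Assumptions: EFS stands in for PFS; hazards are constant; *s*, the share of first events that are deaths without progression, is not in the documents and runs from 10% to 50%.

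The cumulative hazard of a first event over 3 years is −ln(0.78) = 0.2485. If every patient is censored at progression, the Kaplan-Meier OS at 3 years estimates exp(−0.2485·s) = 0.78^s. The death rate after progression is solved so that true 3-year OS is 88%.

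| s | Estimated OS, all progressors censored | Bias (points) | Bias, half still followed | Implied death rate after progression, per year (median survival) |
|---|---|---|---|---|
| 10% | 97.5% | +9.5 | +4.4 | 0.496 (17 months) |
| 20% | 95.2% | +7.2 | +3.4 | 0.400 (21 months) |
| 30% | 92.8% | +4.8 | +2.3 | 0.298 (28 months) |
| 40% | 90.5% | +2.5 | +1.2 | 0.186 (45 months) |
| 50% | 88.3% | +0.3 | +0.2 | 0.062 (134 months) |

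The bias is zero at s = ln(0.88)/ln(0.78) = 51%. There the death rate after progression equals that before it, −ln(0.88)/3 = 0.043 per year.

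*Sensitivity to the proxy.* EFS also counts treatment stops, so PFS may have been higher than 78%. At s = 40%, 0.82^0.4 = 92.4% (bias +4.4) and 0.85^0.4 = 93.7% (bias +5.7). The zero points move to s = 64% and 79%.

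*Deaths reported, living progressors not contacted.* Simulating 400,000 patients with administrative censoring between 3 and 6 years gives 87.4% to 87.7%, a bias of about −0.3 to −0.6 points.

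*Scale.* The binomial SE of OS is √(0.88 × 0.12/35) = 5.5 points. Patients progressed by 3 years: 35 × 0.22 × (1 − s), from 6.9 at s = 10% to 3.8 at s = 50%.

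**Step 3: size of the PFS effect.** Let *k* of 35 patients be removed with stable disease, with 3-year PFS of 78% in the others. Censoring the *k* patients gives 78%. Counting them as failures gives (35 − k)/35 × 78%, which is 75.8% for k = 1 and 73.5% for k = 2. The gap is therefore at most about 2.2 points per patient, against an SE of √(0.78 × 0.22/35) = 7.0 points.

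**The case against.** The strongest reply is that the 5-year sentence in section 3.2 is specific to OS, has no exception for progression and reaches past the last scheduled visit. It could therefore be a vital-status request separate from the visit phase that section 9.1.7 ends. That reading is reasonable and would remove the bias, but no section states it and none provides a contact to carry it out.

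Second, deaths might still arrive by other routes. Section 11.2.2 makes any death of a study subject a serious adverse event, and section 13.2 requires deaths to be reported to the ethics committee. Neither clearly covers a patient already withdrawn, and section 9.1.1 limits adverse-event monitoring to 30 days after treatment. If those routes did work while living progressors went uncontacted, the bias would be slightly negative. The upward direction is therefore conditional on deaths after progression being lost.

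Third, the largest figures need every progressor lost and a low share of deaths without progression, in a disease that section 1.1.1 describes as one of older men. At a share of 30% or more the bias is below one SE. This limits the size, but a systematic error is not excused by a wide interval. The calculation also covers loss at progression only. For treatment stopped through toxicity or preference, neither size nor direction has been shown.

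Fourth, the PFS sentence is generic response-criteria text, and stable-disease patients may be very few because section 4.2 requires orchiectomy and admits fully resected patients. EFS already counts their removal as an event. This is why PFS is the lesser point.

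**Conclusion.** The concern holds. The protocol gives incompatible instructions on survival follow-up after progression, non-response or treatment stop, and gives study withdrawal no fixed meaning. If the stopping instructions are followed and later deaths are missed, 3-year OS is probably biased upward. The illustration gives +9.5 to +0.3 points with every progressor lost and +4.4 to +0.2 with half followed, for an assumed 10% to 50% share of deaths without progression. The bias disappears if item 4 of section 3.2 is applied to all patients. The PFS effect is at most about 2.2 points per stable-disease patient, and EFS is not affected.

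The point should be fixed but does not threaten the primary objective, which is safety and feasibility (section 2.1). No stated decision rule depends on OS or PFS. Confidence is moderate, because the actual bias depends on how sites read the text and on shares the documents do not give.

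**What to change.** 1. Reconcile sections 9.1.1, 9.1.7 and 10.3, and the withdrawal wording in 3.2, 6.1.1 and 9.1.4, with the survival follow-up in 3.2. State that progression or stopping treatment ends the scheduled disease visits but not data collection. Align the meaning of completion in 10.1.
2. State that every enrolled patient who has not withdrawn consent is followed for vital status up to 5 years, and for progression if not yet progressed. Give a contact schedule that covers living patients as well as reports of death.
3. In section 9.3.1, state that PFS does not censor stable-disease patients at removal but follows them to progression or death. Add a sensitivity analysis that counts removal as an event.

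The treatment-stopping rules are not at issue and need not change.

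**Cost.** Protocol wording, plus vital-status contacts for about 4 to 7 progressed patients of 35 (by the assumptions above) and for those who stop early. Contact to year 5 is already implied by section 3.2. If treatment ends at about week 30 (6.9 months), the study ends 6.9 + 36 = 42.9 months after the last enrolment, 17.1 months short of 60. With even accrual, 17.1/36 × 35 = 16.6 patients would not yet have reached 5 years, or 17.1/48 × 35 = 12.5 with the 4-year accrual in the synopsis. The OS and PFS estimates would probably be less favourable.

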### **Minimal evaluations at months 3, 9, 15, 21 and 30**

- Physical examination
- Recent clinical history
- ECOG performance status
- Hematology (hemoglobin, WBC and differential, Platelets)
- Blood chemistry (AST, ALT, ALP, creatinine, serum LDH, total bilirubin, albumin)
- Additional assessments if clinically indicated

### **Extensive evaluations at months 6, 12, 18, 24 and 36**

- Recent clinical history
- Physical examination (size of lymph nodes, sign of organ involvement)
- ECOG performance status
- Chest and abdomen computer tomography; CT of the head and neck at the discretion of the treating physician
- Testicular ultrasound
- Hematology (hemoglobin, WBC and differential, Platelets)
- Blood chemistry (AST, ALT, ALP, total bilirubin, creatinine, albumin)
- Clearance creatinine
- Serum LDH
- Beta-2-microglobulin
- IgA, IgG, IgM
- Additional assessments if necessary according to the local standards and if clinically indicated at the discretion of the treating physician

## 9.2. Pathology review

The work of the pathologist is essential for the success of this study and includes diagnosis and classification of the lymphoma according to the WHO classification criteria.

The local pathologist of each center participating in this trial has to be informed by the local investigator about the trial protocol, particularly about data and sample processing. The IELSG Lymphoma Review Center will review all cases.

After examination by the local pathologist, paraffin block should be sent for central pathology review and additional pathological studies to the IELSG Lymphoma Review Center (LRC) at the IELSG Coordinating Center.

In addition, a copy of original report(s) including diagnosis, classification and immunophenotyping by the local pathologist will be sent by fax or e-mail to the IELSG coordinating center. If possible, diagnostically relevant clinical data (i.e., peripheral blood examination, bone marrow aspiration cytology, immunoelectrophoresis) should be added. In case of doubt the LRC may request paraffin embedded material to complement the analysis.

## 9.3. Endpoint definitions

Overall Response Rate (ORR): Complete Remission, Complete Remission Unconfirmed, Partial Remission.

A patient is defined as a responder if he has a complete or partial response. Patients without response assessment (due to whatever reason) will be considered as non-responder.

### 9.3.1. Criteria for evaluation

The recently published recommendations of an International Workshop to Standardise Response Criteria for Non-Hodgkin's Lymphomas [Cheson et al., 2007 Journal Clinical Oncology 25: 579-586] will be applied.

Response criteria will be determined as follows:

**Complete response (CR)** is required:

1. Complete disappearance of all detectable clinical evidence of disease and disease-related symptoms if present before therapy.
2. (a) Typically FDG-avid lymphoma: in patients with no pre-treatment PET scan or when the PET scan is positive before therapy, a post-treatment residual mass of any size is permitted as long as it is PET negative.  
(b) Variably FDG-avid lymphomas /FDG avidity unknown: in patients without a pre-treatment PET scan, or if a pre-treatment PET scan was negative, all lymph nodes and nodal masses must have regressed on CT to normal size ( $\leq 1.5$  cm in their greatest transverse diameter for nodes  $> 1.5$  cm before therapy). Previously involved nodes that were 1.1 to 1.5 cm in their long axis and more than 1.0 cm in their short axis before treatment must have decreased to  $\leq 1.0$  cm in their short axis after treatment.
3. The spleen and/or liver, if considered enlarged before therapy on the basis of a physical examination or CT scan, should not be palpable on physical examination and should be considered normal size by imaging studies, and nodules related to lymphoma should disappear. However, determination of splenic involvements not always reliable because a spleen considered normal in size may still contain lymphoma, whereas an enlarged spleen may reflect variations in anatomy, blood volume, the use of hematopoietic growth factors, or causes other than lymphoma.
4. If the bone marrow was involved by lymphoma before treatment, the infiltrate must have cleared on repeat bone marrow biopsy. The biopsy sample on which this determination is made must be adequate (with a goal of  $> 20$  mm unilateral core). If the sample is indeterminate by morphology, it should be negative by immunohistochemistry. A sample that is negative by immunohistochemistry but that

demonstrates a small population of clonal lymphocytes by flow cytometry will be considered a CR until data become available demonstrating a clear difference in patient outcome.

**Partial Remission (PR) is required:**

1. At least a 50% decrease in sum of the product of the diameters (SPD) of up to six of the largest dominant nodes or nodal masses. These nodes or masses should be selected according to all of the following: they should be clearly measurable in at least 2 perpendicular dimensions; if possible they should be from disparate regions of the body; and they should include mediastinal and retroperitoneal areas of disease whenever these sites are involved.
2. No increase should be observed in the size of other nodes, liver, or spleen.
3. Splenic and hepatic nodules must regress by  $\geq 50\%$  in their SPD or, for single nodules, in the greatest transverse diameter.
4. With the exception of splenic and hepatic nodules, involvement of other organs is usually assessable and no measurable disease should be present.
5. Bone marrow assessment is irrelevant for determination of a PR if the sample was positive before treatment. However, if positive, the cell type should be specified (e.g. large-cell lymphoma or small neoplastic B cells). Patients who achieve a CR by the above criteria, but who have persistent morphologic bone marrow involvement will be considered partial responders. When the bone marrow was involved before therapy and a clinical CR was achieved, but with no bone marrow assessment after treatment, patients should be considered partial responders.
6. No new sites of disease should be observed.
7. Typically FDG-avid lymphoma: for patients with no pretreatment PET scan or if the PET scan was positive before therapy, the post-treatment PET should be positive in at least one previously involved site.
8. Variably FDG-avid lymphomas/FDG-avidity unknown: for patients without a pretreatment PET scan, or if a pretreatment PET scan was negative, CT criteria should be used.

**Stable Disease (SD) is required:**

1. A patient is considered to have SD when he or she fails to attain the criteria needed for a CR or PR, but does not fulfil those for progressive disease (see Relapsed Disease [after CR]/Progressive Disease [after PR, SD]).
2. Typically FGD-avid lymphomas: the PET should be positive at prior sites of disease with no new areas of involvement on the post-treatment CT or PET.
3. Variably FDG-avid lymphomas/FDG-avidity unknown: for patients without a pretreatment PET scan or if the pretreatment PET was negative, there must be no change in the size of the previous lesions on the post-treatment CT scan.

**Relapsed Disease (after CR) / Progressive Disease (after PR, SD)**

Lymph nodes should be considered abnormal if the long axis is more than 1.5 cm regardless of the short axis. If a lymph node has a long axis of 1.1 to 1.5 cm, it should only be considered abnormal if its short axis is more than 1.0 cm. Lymph nodes  $\leq 1.0 \times \leq 1.0$  cm will not be considered as abnormal for relapse or progressive disease.

1. Appearance of any new lesion more than 1.5 cm in any axis during or at the end of therapy, even if other lesions are decreasing in size. Increased FDG uptake in a previously unaffected site should only be considered relapsed or progressive disease after confirmation with other modalities. In patients with no prior history of pulmonary lymphoma, new lung nodules identified by CT are mostly benign. Thus, a therapeutic decision should not be made solely on the basis of the PET without histologic confirmation.
2. At least a 50% increase from nadir in the SPD of any previously involved nodes, or in a single involved node, or the size of other lesions (e.g. splenic or hepatic nodules). To be considered progressive disease, a lymphnode with a diameter of the short axis of less than 1.0 cm must increase by  $\geq 50\%$  and to a size of 1.5 x 1.5 cm or more than 1.5 cm in the long axis.

3. At least a 50% increase in the longest diameter of any single previously identified node more than 1 cm in its short axis.
4. Lesions should be PET positive if observed in a typical FDG-avid lymphoma or the lesion was PET positive before therapy unless the lesion is too small to be detected with current PET systems (< 1.5 cm in its long axis by CT).
5. Measurable extranodal disease should be assessed in a manner similar to that for nodal disease. For these recommendations, the spleen is considered nodal disease. Disease that is only assessable (e.g. pleural effusions, bone lesions) will be recorded as present or absent only, unless, while an abnormality is still noted by imaging studies or physical examination, it is found to be histologically negative.
6. In clinical trials where PET is unavailable to the vast majority of participants, or where PET is not deemed necessary or appropriate for use (e.g. a trial in patients with MALT lymphoma), response should be assessed as above, but only using CT scans. However, residual masses should not be assigned CRu status, but should be considered partial responses.

**Overall survival** will be determined from the date of enrollment into the study to the date of death from any cause. Patients who have not died at the time of the final analysis will be censored at the date of the last contact.

**Event-free survival (time to treatment failure)** is measured from the time from study entry to any treatment failure including disease progression, or discontinuation of treatment for any reason (e.g. disease progression, toxicity, patient preference, initiation of new treatment without documented progression, or death). It may be useful in the evaluation of some therapies such as those that are highly toxic.

**Progression-free survival PFS** is defined as the time from entry onto a study until lymphoma progression or death as a result of any cause. PFS is the preferred end point in lymphoma involving incurable histologic subtypes clinical trials (e.g. follicular, other low-grade lymphoma, or mantle cell lymphoma). In studies in which failure to respond without progression is considered an indication for another therapy, such patients should be censored at that point for the progression analysis.

**Disease-Free Survival** is measured from the time of occurrence of disease-free state or attainment of a CR to disease recurrence or death as a result of lymphoma or acute toxicity of treatment. This definition may be complicated by deaths that occur during the follow-up period that are unrelated to the lymphoma, and there is controversy about whether such deaths should be considered as events or censored at the time of occurrence. Although it is often possible to identify those deaths related to the lymphoma, there is the potential for bias in the attribution of deaths.

**Lymphoma-Specific Survival** is defined as time from study entry to death as a result of lymphoma. This end point is potentially subject to bias because the exact cause of death is not always easy to ascertain. To minimize the risk of bias, the event should be recorded as death as a result of lymphoma, or as a result of toxicity from the drug. Death as a result of unknown causes should be attributed to the therapy.

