### 6.2.1. CHOP dose modification

Patients will start R-CHOP every 21 days if neutrophils  $> 1.0 \times 10^9/L$  and platelets  $> 75 \times 10^9/L$ .

- If neutrophils are  $< 1.5 \times 10^9/L$  and/or platelets  $< 75 \times 10^9/L$ : R-CHOP must be delayed (after 7 days, on day +28)
- If Neutrophils  $\geq 1.5 \times 10^9/L$  and Platelets  $\geq 75 \times 10^9/L$  on Day +28 R-CHOP will be performed with no change in dose

In case of neutropenia Filgrastim or Peg-Filgastrim should be added in the following course of chemotherapy according to "2006 update of recommendations for the use of white blood cell growth factors: an evidence-based clinical practice guideline" (Journal Clinical Oncology 2006 24:3187-3205), and to primary physician judgment in order to avoid delay. Primary prophylaxis of neutropenia with filgastrim or peg-Figastim is allowed in patients over 65 years of age according to the same guidelines.

- Dose modification for sensory neuropathy. No modification as long as neuropathy does not affect function. Any decrease of function (grade 3/4) would lead to dose reduction of vincristine by 50%. If grade 4 toxicity persists after reduction of vincristine by 50%, vincristine may be eliminated from subsequent cycles.
- Prednisone dose may be decreased by 50% or discontinued if patients have increase in serum glucose to  $> 300 \text{ mg/dl}$ , or other psychological disturbances such as psychosis or anxiety attacks.

Just patients who have achieved PR/CR after three cycles of CHOP will continue therapy. All other patients will be removed from the study and will be considered for other possible therapies according to the local policy.

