### **10.2. Discontinuation of Treatment**

A patient should be discontinued from study treatment based on:

- Investigator discretion based on safety issues
- Progressive disease
- No response after the third course of therapy
- Any  $\geq$  grade 3 toxicity for > 2 weeks

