### **10.3. Withdrawal From the Study**

A subject will be withdrawn from the study for any of the following reasons:

- Lost at follow-up
- Consent withdrawal
- Discontinuation of study treatment (final assessments will be obtained) if applicable

When a subject withdraws before completing the study, the reason for withdrawal is to be documented on the CRF and in the source document. Study drug assigned to the withdrawn subject may not be assigned to another subject.

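### The PFS definition censors patients who fail to respond without progressing; here that covers stable disease after course 3, so 3-year PFS may be biased upward if such patients occur

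*Combined protocol and SAP*

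**What the plan says.** The only PFS definition is in section 9.3.1. An event is progression or death from any cause, counted from study entry. The definition then deals with studies in which a patient who neither responds nor progresses would be moved to another therapy: "such patients should be censored at that point for the progression analysis".

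Three sections describe what happens to such patients here:

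- Section 6.2.1 lets only patients in PR or CR continue after three cycles. "All other patients will be removed from the study and will be considered for other possible therapies according to the local policy".
- Section 9.1.4, on the interim restaging: "All patients in SD/PD will be withdrawn from the study and evaluated as treatment failure".
- Section 10.2 lists among the reasons for stopping treatment: "No response after the third course of therapy".

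On later follow-up the sections disagree. Section 3.2 says: "Patients will be followed for disease progression and survival until the end of the study". Section 9.1.1 says: "Follow-up will continue until disease progression (PD), patient withdrawal, death or the study completion". Section 10.3 lists as a reason for withdrawal: "Discontinuation of study treatment (final assessments will be obtained) if applicable". Section 9.1.7 has its own stopping rule: "The follow up phase will end in case of dead or progressive disease". Section 10.1 classes patients who stop for lack of efficacy as having completed the study.

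Section 2.2 makes 3-year PFS and 3-year EFS secondary objectives, to be compared with historical treatment. Section 3.1 gives no analysis rules for PFS, and no sensitivity analysis is planned.

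**The concern.** Section 9.3.1 defines SD as neither response nor progression. An SD patient at the interim restaging is therefore the patient the censoring sentence describes, and this trial satisfies its condition. Followed literally, the plan takes these patients out of the PFS risk set after three courses, and nothing elsewhere overrides that for PFS.

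The documents name no estimator. Kaplan-Meier, the usual choice, assumes that a censored patient has the same future risk as those still under observation. Here the censoring is triggered by failure of the study regimen. If SD patients later progress or die more often than the rest, their events are lost and 3-year PFS comes out too high. That is the favourable direction for the single-arm result.

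The conflict over follow-up makes this worse. If sites apply sections 9.1.1 and 10.3, later progressions in these patients may never be recorded, and no reanalysis could recover them. Deaths, and so overall survival, could be affected in the same way.

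**Working it through.** **Does the rule apply?** SD fails the CR and PR criteria without meeting those for progression (9.3.1). SD after course 3 leads to removal and consideration of other therapy (6.2.1, 9.1.4, 10.2). The condition is met. Patients with progression at the interim restaging remain PFS events, so only SD is affected.

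**When does censoring fall?** Attachment 9 puts course 3 at day 42 and course 4 at day 63, with the restaging between them. Censoring is therefore at about day 63 of a 3-year endpoint.

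**Inputs.** N = 35 is the planned enrolment. The documents give no expected 3-year PFS for this trial, no SD rate and no SD outcome, so there is no figure in the plan to reproduce and the following are assumptions:

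- E = true progressions or deaths by 3 years: 10, varied from 8 to 12
- k = SD patients at the interim restaging: 0 to 3
- s = 3-year PFS of SD patients: 30%, or 0% as the worst case

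**Formulas.** Take the SD patients as censored before any other event, with everyone else followed for 3 years:

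- true PFS = (35 − E)/35
- reported PFS = (35 − E − s·k)/(35 − k)
- equivalently, bias = (k/35) × (PFS of the others − s)

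**Results for E = 10.** True PFS = 25/35 = 71.4%. Standard error = √(0.714 × 0.286/35) = 7.6 points.

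| k | s = 30% | bias (points) | s = 0% | bias (points) |
|---|---|---|---|---|
| 0 | 71.4% | 0 | 71.4% | 0 |
| 1 | 24.7/34 = 72.6% | +1.2 | 25/34 = 73.5% | +2.1 |
| 2 | 24.4/33 = 73.9% | +2.5 | 25/33 = 75.8% | +4.3 |
| 3 | 24.1/32 = 75.3% | +3.9 | 25/32 = 78.1% | +6.7 |

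Across E = 8 to 12, each SD patient adds about 1.1 to 1.5 points (s = 30%) or 1.9 to 2.4 points (s = 0%). The largest total is at E = 8, k = 3, s = 0%: 27/32 − 27/35 = 84.4% − 77.1% = 7.2 points, against a standard error of 7.1 points.

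**Other assumptions.** With three SD patients at 25% 3-year PFS, the bias is 2.1, 3.9 or 4.5 points when the others' PFS is 50%, 70% or 78%. For example, (3/35) × (70 − 25) = 3.9. With five SD patients and others' PFS at 70%, it is 6.4 points (s = 25%) or 10.0 points (s = 0%). If SD patients do as well as the others, it is zero.

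**Simulation check.** Kaplan-Meier simulation with 35 patients, 3 of them SD, and others' PFS at 70% gave 70.3% when SD was censored. It gave 66.5% when SD patients were followed (25% progression-free 36 months after the restaging), and 64.2% when SD counted as an event. The first gap, 3.8 points, agrees with the formula.

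**The case against.** The strongest reply is that the sentence is general guidance that came with the endpoint definitions. The same paragraph discusses low-grade lymphomas, and the wording is conditional. The trial-specific text in 9.1.4 calls these patients treatment failures, so the plan is arguably unclear rather than committed to censoring. This has some force. But section 9.3.1 says the published criteria will be applied, it holds the only PFS definition, and its condition is met. The treatment-failure label matches the EFS definition, not the PFS one. If the sentence was not meant to operate, deleting it is still the right correction.

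Second, the effect may be nil. Orchiectomy is mandatory, patients with all disease removed are eligible (4.2), and SD needs residual disease to assess. The primary objective is safety and feasibility, no PFS test or threshold is set, and 3-year EFS already counts these patients as failures. All of this stands and limits the importance of the point. It does not make EFS a substitute: EFS also counts stops for toxicity or preference, and section 2.2 names PFS separately.

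Third, deleting the sentence alone would achieve little if follow-up ends at withdrawal, because the patients would then be censored at about the same time. That is right, so the correction has to cover follow-up too. Section 9.1.7 does not cut an SD patient off before a PFS event; it matters only for survival after progression.

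**Conclusion.** The concern holds, in its conditional form. As written, the plan censors SD patients for PFS because the study regimen failed them, and 3-year PFS is overstated if they occur and fare worse than the rest. For one to three such patients among 35, with 10 true events, the overstatement is 1.2 to 3.9 points at an assumed 30% SD outcome, and 2.1 to 6.7 points if all of them fail. For up to three patients, even the extreme case across 8 to 12 events is about one standard error. The number of SD patients and their prognosis are assumptions; with none, there is no bias.

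The primary objective is untouched. The net effect on the historical comparison is unknown, because the documents give no 3-year historical PFS and do not say how the earlier studies censored non-responders. The point should be corrected, since the error runs in one direction and lost follow-up could not be recovered later.

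**What to change.** 1. Delete the censoring sentence from the PFS definition in 9.3.1. State that the first progression or death counts whenever it occurs, and that stopping study treatment or starting another therapy is neither an event nor a reason for censoring.
2. Reconcile sections 3.2, 6.2.1, 9.1.1, 9.1.4, 9.1.7 and 10.3, together with 10.1, so that stopping treatment does not end follow-up for progression and survival. Only withdrawal of consent or loss to follow-up should do so.
3. Add one sensitivity analysis that counts SD withdrawal at the interim restaging as a PFS event.

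The clinical rule on who stops treatment stays as it is. The cost is one deleted sentence, aligned wording in seven sections, one short extra analysis and a little more follow-up of non-responders. The PFS estimate may come out slightly less favourable.
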